5.1 Imputation rules

5.1.1 Study drug

Not applicable

5.1.2 AE date imputation

AE date imputation is based only on a comparison of the partial AE start date to the treatment start date as mentioned in the Table 1-2 below.

1. If the AE start date year value is missing, the date uncertainty is too high to impute a rational date. Therefore, if the AE year value is missing, the imputed AE start date is set to NULL.
2. If the AE start date year value is less than the treatment start date year value, the AE started before treatment. Therefore:

- a. If the AE year is less than the treatment year and the AE month is missing, the imputed AE start date is set to the mid-year point (01JulYYYY).
- b. Else, if the AE year is less than the treatment year and the AE month is not missing, the imputed AE start date is set to the mid-month point (15MONYYYY).

3. If the AE start date year value is greater than the treatment start date year value, the AE started after treatment. Therefore:

- a. If the AE year is greater than the treatment year and the AE month is missing, the imputed AE start date is set to the year start point (01JanYYYY).
- b. Else, if the AE year is greater than the treatment year and the AE month is not missing, the imputed AE start date is set to the month start point (01MONYYYY).

4. If the AE start date year value is equal to the treatment start date year value:

- a. And the AE month is missing or the AE month is equal to the treatment start month, the imputed AE start date is set to one day after treatment start.
- b. Else, if the AE month is less than the treatment start month, the imputed AE start date is set to the mid-month point (15MONYYYY).
- c. Else, if the AE month is greater than the treatment start month, the imputed AE start date is set to the start month point (01MONYYYY).

Table 5.1-2: AE start date imputation

	MON	MON < CFM	MON = CFM	MON > CFM
	MISSING			
YYYY MISSING	NULL	NULL	NULL	NULL
	Uncertain	Uncertain	Uncertain	Uncertain
YYYY < CFY	(D) = 01JULYYYY	(C)= 15MONYYYY	(C)= 15MONYYYY	(C)= 15MONYYYY
	Before Treatment Start	Before Treatment Start	Before Treatment Start	Before Treatment Start
YYYY = CFY	(B)= TRTSTD+1	(C)= 15MONYYYY	(A)= TRTSTD+1	(A)= 01MONYYYY
	Uncertain	Before Treatment Start	Uncertain	After Treatment Start
YYYY > CFY	(E)= 01JANYYYY	(A)= 01MONYYYY	(A)= 01MONYYYY	(A)= 01MONYYYY
	After Treatment Start	After Treatment Start	After Treatment Start	After Treatment Start
Before Treatment Start	Partial indicates date prior to Treatment Start Date			
After Treatment Start	Partial indicates date after Treatment Start Date			
Uncertain	Partial insufficient to determine relationship to Treatment Start Date			
LEGEND:				
(A)	MAX(01MONYYYY,TRTSTD+1)			
(B)	TRTSTD+1			
(C)	15MONYYYY			

(D)	01JULYYYY
(E)	01JANYYYY

AE end date imputation

For the purpose of date imputation, the study treatment follow-up period date is defined as the last available visit date, i.e. including unscheduled visits after the end of study visit.

1. If the AE end date month is missing, the imputed end date should be set to the earliest of the (study treatment follow-up period date, 31DECYYYY, date of death).
2. If the AE end date day is missing, the imputed end date should be set to the earliest of the (study treatment follow-up period date, last day of the month, date of death).
3. If AE year is missing or AE is ongoing, the end date will not be imputed.

If the imputed AE end date is less than the existing AE start date then use AE start date as AE end date.

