1.1 Study design

This is a 52-week, randomized, double-blind, double-dummy, placebo-controlled, multicenter study to assess the efficacy of secukinumab 150 mg or 300 mg in patients with AxPsA who have had an inadequate response to two different NSAIDs. The study will consist of two treatment periods; a double-blind placebo-controlled period from Baseline to Week 12 followed by a double-blind secukinumab treatment period from Week 12 to Week 52.

The schematic of study design is given in Figure 1.1 below.

Planned number of patients and randomization

A total of 495 patients (165 patients per group) will be recruited to compensate dropouts and protocol violators.

Patient eligibility will be assessed during a maximum screening period of 8-weeks. At Baseline, all patients whose eligibility is confirmed will be randomized in a 1:1:1 ratio to secukinumab 150 mg, secukinumab 300 mg or placebo. At Week 12, patients randomized to placebo at Baseline will be re-randomized (1:1) to active treatment with secukinumab 150 mg or secukinumab 300 mg.

Group 1: secukinumab 150 mg

Treatment Period 1

secukinumab 150 mg (1 × 1.0 mL prefilled syringes (PFS)) + placebo (1 × 1.0 mL PFS) at Baseline, Week 1, 2, 3 and 4, then 4 weeks later at Week 8.

Treatment Period 2

secukinumab 150 mg (1 × 1.0 mL PFS) + placebo (1 × 1.0 mL PFS) administered every 4 weeks from Week 12 to Week 52 (last dose on Week 48).

Group 2: secukinumab 300 mg

Treatment Period 1

secukinumab 300 mg (2 × 1.0 mL PFS) administered at Baseline, Week 1, 2, 3 and 4, then 4 weeks later at Week 8.

Treatment Period 2

secukinumab 300 mg (2 × 1.0 mL PFS) administered every 4 weeks from Week 12 to Week 52 (last dose on Week 48).

Group 3: placebo

Treatment Period 1

placebo (2 × 1.0 mL PFS) administered at Baseline, Week 1, 2, 3 and 4, then 4 weeks later at Week 8.

Treatment Period 2

secukinumab 150 mg (1 × 1.0 mL PFS) + placebo (1 × 1.0 mL PFS) administered every 4 weeks from Week 12 to Week 52 (last dose on Week 48), OR

secukinumab 300 mg (2 × 1.0 mL PFS) administered every 4 weeks from Week 12 to Week 52 (last dose on Week 48).

[figure not shown]
Patients, investigator staff, persons performing the assessments and data analysts will remain blinded to the identity of the treatment from the time of randomization until database lock. No stratification at randomization will be performed.

Primary analysis time point

The primary and key secondary analyses will be performed at Week 12.

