2.1.1 General definitions

Study treatment: Study treatment refers to:

Secukinumab 150 mg provided in 1 ml PFS or Secukinumab placebo provided in 1 ml PFS.

Study treatment start and end date: Study treatment start date is defined as the first date when a non-zero dose of study drug is administered and recorded on the Drug Administration Record (DAR) CRF page. Similarly, study drug end date is defined as the last date when a non-zero dose of study drug is administered and recorded on the DAR CRF page of the core study.

Study day: Study day will be calculated as (event date – study drug start date + 1 day) for events that occurred on or after study drug start date (e.g., visit, lab samples, AEs). For events prior to study drug start date (e.g., time of diagnosis), study day will be negative and calculated as (event date – study drug start date). Note that study drug start date is study day 1 and the day before study drug start date is study day -1 (i.e. no study day 0).

Due to the study drug dosing schedule, one month will be considered as 28 days. However, for “time since event” data (e.g., medical history), one month will be considered as 365.25/12 days for events that occurred prior to study Day 1. Time from events prior to the start of study drug, e.g., time since diagnosis, is calculated as the difference between the start date of study drug and the date of prior event.

Note that, the first dose day is Day 1, and the day before the first dose day is counted as Day -1 (not Day 0).

Baseline and post baseline: In general, a *baseline* value refers to the last measurement made prior to administration of the first dose of study treatment. A post-baseline value refers to a measurement taken after the first dose of study treatment.

Treatment Period: There are 2 treatment periods for this study defined as:

Treatment Period 1 is defined as a 12 Week placebo-controlled, double-blind treatment period starting from baseline till Week 12.

Treatment Period 2 is a 40 Week double-blinded active treatment period starting from Week 12 till Week 52.

Lost to follow up: The patients, whose study completion status is unclear, because they fail to appear for study visits without stating an intention to withdraw.

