5.4.3 Exposure adjusted incidence rate and 100*(1- α) % confidence interval

It will be assumed that for each of n subjects in a clinical trial the time t_j ($j=1, \dots, n$) to the first occurrence of a certain event is observed, or if the event was not experienced, the (censored) time to the end of the observation period. The sequence of first occurrences of an event will be modeled to follow approximately a Poisson process with constant intensity θ . The rate parameter θ will be estimated as $\lambda=D/T$, where

$$T = \sum_{j=1}^n t_j$$

and D is the number of subjects with at least one event. Conditionally on T, an exact 100*(1- α)% confidence interval for a Poisson variable with parameter θT and observed value D can be obtained based on (Garwood 1936), from which an exact 100*(1- α)% confidence interval for D/T will be derived as follows (Sahai 1993; Ulm 1990):

$$\text{Lower confidence limit } L = \frac{0.5c_{\alpha/2,2D}}{T} \text{ for } D>0, 0 \text{ otherwise,}$$

$$\text{Upper confidence limit } U = \frac{0.5c_{1-\alpha/2,2D+2}}{T}$$

where $c_{\alpha,k}$ is the α th quantile of the Chi-square distribution with k degrees of freedom.

The example below shows how this should be handled for cases where subjects switch treatment. In particular for summarizing 'Any AIN' as a group, one should take into consideration the sequence of treatments while calculating exposure time for subjects.

Table 16-3 Examples for calculating exposure time for incidence rates (IR)

1st treatment	1st exposure	2nd treatment	2nd exposure	Event days (in terms of study day)	Exposure for IR
Placebo	100 days	150 mg	200 days	50 (1st trt) 110 (10 days into 2nd trt)	Placebo: 50 days (event) 150 mg: 10 days (event) Any AIN: 10 days (event)

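### In placebo patients who switch at Week 12, every partial AE start date that straddles the switch is credited to placebo, never to secukinumab

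*SAP*

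**What the plan says.** Section 5.1.2 has one reference date: "AE date imputation is based only on a comparison of the partial AE start date to the treatment start date". Section 2.1.1 defines it: "Study treatment start date is defined as the first date when a non-zero dose of study drug is administered". The same section lists study treatment as "Secukinumab 150 mg provided in 1 ml PFS or Secukinumab placebo provided in 1 ml PFS", so for Group 3 the reference is the first placebo dose.

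Section 1.1 gives that group a second start: "At Week 12, patients randomized to placebo at Baseline will be re-randomized (1:1) to active treatment". Neither the rules in 5.1.2 nor Table 5.1-2 and its legend mention it.

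If the year equals the start year and the month is missing or equals the start month, "the imputed AE start date is set to one day after treatment start" (rule 4a). For a later month in the start year, "if the AE month is greater than the treatment start month, the imputed AE start date is set to the start month point" (rule 4c). In a later year, the date becomes 1 January if the month is missing (rule 3a) and the first of the month if it is known (rule 3b).

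For attribution, Section 2.1 allows a patient to count in more than one treatment group in exposure-adjusted analyses of the entire period. Section 5.4.3 gives a worked case: "The example below shows how this should be handled for cases where subjects switch treatment". There the event day decides whether the event belongs to placebo or to secukinumab.

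**The concern.** One third of patients (165 of 495) are planned for placebo and have two treatment starts. For them the imputed onset date also decides which treatment the event is charged to. A rule that knows only the first start cannot do this evenly.

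The plan's handling of the first start is cautious: where the relation to the first dose is uncertain, Table 5.1-2 places the event after it, so that it counts as treatment-emergent. At the second start the same rules do the opposite, and the doubtful event is kept away from the active drug. The summaries exposed are the entire-period exposure-adjusted rates of AEs, SAEs and AESIs (Table 2.8-4), any Period 2 tabulation, and the Any AIN group. For a rare AESI, a single event can be visible.

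The early date also acts on the denominator. Under rule 4a the event falls on study day 2, so the patient contributes two days of placebo time at risk for that event.

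**Working it through.** **The plan's own figure.** In the 5.4.3 example, placebo lasts 100 days and an event occurs on study day 110. Exposure on 150 mg to that event is 110 − 100 = 10 days, as stated. Onset day decides attribution.

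**Direction.** For an onset after the first dose, rules 3a, 3b, 4a and 4c (with legend A) each return the earliest day that fits both the partial date and a post-start onset. Two things follow.
- A partial date that straddles the switch includes the day before it, so its earliest compatible day lies in the placebo period.
- The imputed day is never later than the true onset, so no placebo-period event can move to secukinumab.

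**Example.** First dose 22 Jan 2018; Day 85 is 16 Apr 2018. An AE dated Apr 2018 becomes 1 Apr 2018, study day 70: placebo. An AE dated 2018 becomes 23 Jan 2018, study day 2: placebo.

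**Size per partial date.** Inputs: switch on Day 85 (scheduled Week 12 day, Table 2-1), with Days 72 and 104 (the Week 12 window) as the range. Assumptions: first-dose dates spread evenly over the calendar and onset uniform over Days 2 to 365. That gives 83 placebo days (2 to 84) and 281 secukinumab days (85 to 365).

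*Month known, day missing.* If the switch falls on day j of a month of length L, L − j + 1 days lie on or after it and j − 1 before it; j = 1 does not straddle. Averaged over j, each side has (L − 1)/2 days. With L = 30.44 this is 14.7 days.
- Secukinumab onsets moved to placebo: 14.7/281 = 5.2%.

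*Only the year known.* If the switch falls on day s of a 365-day year, the secukinumab onsets in that year number min(281, 366 − s), and all move to placebo unless s = 1.
- Sum over s: 85 × 281 + (280 × 281)/2 − 281 = 62,944.
- Mean: 62,944/365 = 172.4 days, and 172.4/281 = 61.4%.

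A full enumeration of first-dose dates over an assumed four-year calendar (2017 to 2020) agrees:

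| Partial date | Straddling dates sent to secukinumab | Secukinumab onsets sent to placebo (Day 85) | Range, Day 72 to Day 104 |
|---|---|---|---|
| Day missing | 0 of 43,040 | 5.2% | 5.0% to 5.6% |
| Day and month missing | 0 of 359,376 | 61% | 60% to 64% |

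With the day missing, the share is 52% among onsets in the first 28 days after the switch. No placebo onset moved to secukinumab in any run.

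**Effect of a second reference date.** Suppose straddling dates are set to the day after the switch. No secukinumab onset is then lost, and the error reverses.
- Month known: 14.7/83 = 17.7% of placebo onsets move to secukinumab. In days, 14.7 are misassigned under either rule.
- Year only: placebo onsets in the switch year number min(83, s − 1). The sum is 83 × 282 + (82 × 83)/2 = 26,809; the mean is 73.4 days, or 73.4/83 = 88.5%. In days, 73.4 are misassigned against 172.4 under the current rule.

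Total misassignment is therefore unchanged for month-only dates and lower for year-only dates, before any use of end dates.

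**The case against.** A reader might infer that the rule inflates placebo rates in the Day 1 to Week 12 tables and so flatters secukinumab in the randomised comparison. The documents do not support this. The rules depend on the first-dose date and the partial date, not on the arm. Groups 1 and 2 have the same reference and the same Week 12 boundary, so their straddling events are pulled back into Period 1 as well.

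A reader might also want a count of affected events. The SAP gives neither an AE frequency nor a share of partial dates. As pure assumption, take 1,000 secukinumab-period onsets in switchers with 4% month-only dates: 40 × 0.052 = 2.1 are moved. Year-only dates add 0.6 at a share of 0.1% and 6.1 at 1%. The total runs from 2.7 to 8.2 and depends mainly on the year-only guess. Moreover, 5.4.3 counts patients with at least one event, so a moved event changes a numerator only where the patient has no other qualifying event in that period. That the effect is small stands as a fair objection.

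Two textual defences are weaker. Section 2.8.1 leaves date algorithms to programming specifications, which are not at hand. But 5.1.2 states a full rule and says it rests on one comparison only, so a different specification would contradict it. The non-zero dose in 2.1.1 could be read as active drug, but that section lists placebo as study treatment and 2.4.1 speaks of a first placebo dose.

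Finally, a second reference date reverses the error for straddling dates and does not remove it. That is correct and bears on how the fix is framed.

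**Conclusion.** The point holds for treatment attribution in placebo switchers, in the entire-period exposure-adjusted, Period 2 and Any AIN summaries. There every partial date that straddles the first Period 2 dose goes to placebo, and the shift always runs away from the test drug. Dates lying wholly after the switch are placed correctly, and events with no year receive no date at all.

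The direction follows from the rules alone. The percentages in the table rest on uniform onset and evenly spread start dates, and apply per partial date. The number of events cannot be estimated from the SAP and is probably small. The randomised Day 1 to Week 12 comparison is not biased by this rule in itself. The change is worth making because the default in a safety attribution should not favour the active drug by construction, and it costs little.

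**What to change.** Add the first Period 2 dose to Section 5.1.2 as a second reference date, for treatment attribution only. In the entire-period, Period 2 and Any AIN summaries, assign an event in a switcher to secukinumab if its partial start date straddles that dose and its end date does not precede it. For time at risk, the day after that dose would mirror rule 4a. Since 5.1.2 already imputes partial end dates late, the end-date check removes only events that must have ended before the switch.

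Keep the Day 1 to Week 12 tables under one imputation rule, identical in all arms. A rule applied there to placebo patients only would create an imbalance that does not now exist.

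The cost is one added rule and a small change to the date program. Some true placebo events will count under secukinumab, so report the attribution under the current rule as a sensitivity tabulation. The two results then show how far the choice matters. If the programming specifications already contain such a step, bring 5.1.2 into line with them.

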2.8.1 Adverse events (AEs)

The crude rates of treatment emergent adverse events (i.e. events started after the first dose of study treatment or events present prior to the first dose of study treatment but increased in severity based on preferred term, and events until 12 weeks after last dose of study treatment) will be summarized by primary system organ class and preferred term.

In addition, exposure time-adjusted incidence rates including 95% confidence intervals will be provided for the entire treatment period to adjust for differences in exposure. A graphical display of the crude rates and exposure-adjusted incidence rates will be presented for all AEs and serious AEs by system organ class.

Adverse events will be summarized by presenting, for each treatment group, the number and percentage of patients having at least one AE, having an AE in each primary system organ class and having each individual AE (preferred term). Summaries (crude rates only) will also be presented for AEs by severity and for study treatment related AEs. If a particular AE 'severity' is missing, this variable will be listed as missing and treated as missing in summaries. If a subject reported more than one adverse event with the same preferred term, the adverse event with the greatest severity will be presented. If a subject reported more than one adverse event within the same primary system organ class, the subject will be counted only once with the greatest severity at the system organ class level, where applicable.

Separate summaries will be provided for

- adverse events suspected to be related to study drug by the investigator
- deaths
- serious adverse events
- adverse events leading to discontinuation
- adverse events leading to temporary dose interruption.
- adverse events of special interest

Adverse events will also be reported separately by SMQ according to MedDRA, using a narrow search. The MedDRA version used for reporting the study will be described in a footnote.

Follow-up period summaries will be done for all patients in follow-up.

A listing of non-treatment emergent adverse events will be done. These adverse events occurred before the first dose of the study treatment. The crude rates will be provided without treatment information.

For SAEs occurred during screening a listing will be prepared for all patients screened including screening failures.

Algorithms for date imputations will be provided in Programming Specifications.

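### SAP 5.1.2 rule 4a ignores the AE end date, so an event with a partial start date that had already ended before the first dose is counted as treatment-emergent

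*SAP*

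**What the plan says.** Section 5.1.2 limits the inputs of the start-date imputation: "AE date imputation is based only on a comparison of the partial AE start date to the treatment start date". Where the AE year equals the treatment-start year, rule 4a applies if "the AE month is missing or the AE month is equal to the treatment start month", and then "the imputed AE start date is set to one day after treatment start". The accompanying table marks these cells as uncertain, explained as "Partial insufficient to determine relationship to Treatment Start Date".

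The only line that checks start against end stands under the AE end-date rules of the same section: "If the imputed AE end date is less than the existing AE start date then use AE start date as AE end date". It concerns imputed end dates, and it moves the end to the start, never the reverse.

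Section 2.8.1 defines treatment-emergent events as "events started after the first dose of study treatment or events present prior to the first dose" where the latter worsened. It sets no condition on the end date. For events before treatment it plans a separate output: "A listing of non-treatment emergent adverse events will be done. These adverse events occurred before the first dose of the study treatment".

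**The concern.** A start one day after first dose is a reasonable cautious choice when nothing shows whether the event came before or after treatment. It is not reasonable when the record shows that the event was over before any study drug was given. In that case the timing relative to treatment is known, and rule 4a overrides it.

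Such an event leaves the pre-treatment listing of section 2.8.1 and enters the treatment-emergent tables, and the serious-event or special-interest summaries if it qualifies for them. In the exposure-adjusted rates of section 5.4.3 it becomes a first occurrence on study day 2, so the patient's time at risk for that term stops there. The dataset also holds an event with a negative duration, or one whose end date has been rewritten to fit the imputed start.

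**Working it through.** There is no planned figure to reproduce. The rules of 5.1.2 and the definition in 2.8.1 were applied as written to hypothetical records.

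**Step 1: individual records.** Assumed first dose 20MAY2017, so rule 4a gives 21MAY2017.

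| Case | Start recorded | End recorded | Rule | Imputed start | End used | Result |
|---|---|---|---|---|---|---|
| 1 | MAY2017, day missing | 12MAY2017 | 4a | 21MAY2017 | 12MAY2017 | Start 9 days after end; treatment-emergent |
| 2 | 2017, day and month missing | 10APR2017 | 4a | 21MAY2017 | 10APR2017 | Start 41 days after end; treatment-emergent |
| 3 | 2017, day and month missing | APR2017, day missing | 4a | 21MAY2017 | 30APR2017, then reset to 21MAY2017 | Conflict hidden; treatment-emergent |
| 4 | APR2017, day missing | 30APR2017 | 4b | 15APR2017 | 30APR2017 | Correct; not treatment-emergent |
| 5 | APR2017, day missing | 10APR2017 | 4b | 15APR2017 | 10APR2017 | Start 5 days after end; not treatment-emergent |

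Cases 1 to 3 are misclassified. In cases 1 and 2 the consistency line does not act, because the end date is complete and so not imputed. In case 3 it acts and moves the end forward. Case 5 shows that the mid-month rule 4b (and likewise 2b) can also put a start after a recorded end, but there the classification stays right.

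**Step 2: reach of rule 4a.** Inputs: screening of at most 8 weeks = 56 days (SAP 1.1). Assumptions, not in the SAP: onset uniform over a screening period of S days, first dose uniform over a calendar year, exponential duration with mean 5, 10 or 20 days.

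With day and month missing, rule 4a fails to catch a screening onset only if it fell in the previous calendar year. Over all screening onsets that share is [S(S+1)/2] / (365·S) = (S+1)/730. For S = 56: 57/730 = 7.8%, so about 92% are caught. For S = 14: 15/730 = 2.1%, so about 98% are caught.

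With only the day missing, the onset must fall in the first-dose month. Counting every combination of onset and first-dose date for S = 56 gives about 26% of all screening onsets.

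The more relevant denominator is screening events already resolved before first dose. By simulation:

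| Screening length | Day missing (mean duration 5 / 10 / 20 days) |
|---|---|
| 56 days | 21% / 18% / 15% |
| 28 days | 47% / 43% / 41% |
| 14 days | 71% / 70% / 69% |

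With day and month missing, the share at 56 days is 92% / 91% / 91%, and it is higher for shorter screening.

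**Step 3: effect of one affected record on an exposure-adjusted rate.** Assume 165 patients in an arm (SAP 1.1), each followed for 84 days in the first period: 165 × 84 = 13,860 patient-days. The affected patient contributes about 2 days instead of 84, a loss of 82. 82/13,860 = 0.6% of the person-time for that term, plus one spurious event.

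**The case against.** The strongest defence is that rule 4a is a deliberate cautious default. It takes no account of treatment arm, it can add treatment-emergent events but not hide one, and it affects no efficacy result or hypothesis test. All of that stands. It justifies the rule where timing is unknown, but not where a recorded end date settles the matter.

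Secondly, section 2.8.1 leaves date-imputation algorithms to Programming Specifications, which are not shown and may contain an end-date check. That is possible, but such a check would contradict the word that limits the inputs in "AE date imputation is based only on a comparison of the partial AE start date to the treatment start date". The SAP text would still need correcting.

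Thirdly, an affected record needs several things together: an event in screening, a partial start date that meets rule 4a, and an end known to precede first dose. That is a narrow set, and the SAP gives no count. This objection stands in full and limits the importance of the point.

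A reader might infer from the percentages that a large part of the reported treatment-emergent events would be spurious. The documents do not support that. The percentages apply only to resolved screening events that already have a partial start date, and the day-missing figures depend heavily on an assumed screening length, for which the SAP gives only the maximum. A reader might also infer that serious or special-interest counts would be distorted. Nothing in the SAP suggests that any such event has a partial date, and serious events in screening have their own listing in any case.

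**Conclusion.** Rule 4a is wrong as written for one type of record: a partial start date (day missing in the first-dose month, or month missing in the first-dose year) combined with an end before first dose. For each such record the misclassification is certain and follows from the text alone. With a complete end date the start falls after the end; with a partial end date the conflict is concealed, but the event is still counted.

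The consequence is minor. It is confined to safety counts and rates, it errs towards over-reporting, and probably very few records are affected. The shares of about 15–70% (day missing) and over 90% (day and month missing) rest on the uniform-onset, uniform-first-dose and duration assumptions above. They describe the reach of the rule and do not forecast a number of events. The default of treatment start + 1 is not itself at fault where timing is truly unknown.

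**What to change.** Amend 5.1.2 so that the steps run in this order:

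1. Impute a partial AE end date by the existing end-date rules, but without the final consistency line. Those rules take the latest date in the recorded month or year, capped by last visit or death, so such an end falling before treatment start shows that the event was over by then.
2. Impute the start date by rules 1 to 4.
3. If the end date (complete, or imputed in step 1) is earlier than a start imputed under any of rules 2 to 4, set the imputed start to the end date.
4. Treat an event whose end date is before treatment start as not treatment-emergent, and place it in the pre-treatment listing.
5. Keep treatment start + 1 where the end date is missing, the event is ongoing, or the end is after treatment start.

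Step 3 also repairs case 5 and an event ending on the first-dose date, whose start would otherwise fall one day after its end. The SAP should say how that last event is classified, since its imputed start is then the first-dose date.

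The cost is a few sentences in the SAP and a small change to the date-derivation program, including the order of the steps. The downside is that slightly fewer treatment-emergent events are shown.
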